For patients who are randomized and subsequently experience a flare in Period 2, efficacy, health outcomes, and safety data collected between time of flare and the end of Period 2 will be summarized for ixekizumab 80 mg Q2W or ixekizumab Q4W without inferential statistics.

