### **6.1.1. Analysis Populations**

The following analysis populations will be used to address the study objectives.

**Lead-In Period Safety Population:** Unless otherwise specified, safety summaries for Combined Periods 1, 2, and 3 will be conducted on the Lead-In Period Safety Population, defined as all patients who receive at least 1 dose of ixekizumab in Period 1 in RHBY. Patients who do not meet entry criteria for participation in the randomized withdrawal-retreatment period (Group A) will continue to receive ixekizumab 80 mg Q2W or ixekizumab 80 mg Q4W. Patients who meet the entry criteria (Group B) may be randomized to ixekizumab or placebo at Week 24. Patients randomized to placebo may be retreated upon flare with the ixekizumab regimen that they received in Period 1. The data while on placebo is not included in the combined period analysis. For immunogenicity data analysis during the combined periods 1, 2, and 3, all data will be included regardless of being re-randomized to placebo or ixekizumab. Patients will be analyzed according to the treatment they were receiving at the start of Period 1.

**Long-Term Ixekizumab Treatment Efficacy Population:** Unless otherwise specified, efficacy and health outcome for Combined Periods 1, 2, and 3 will be summarized for the Long-Term Ixekizumab Treatment Efficacy Population, defined as patients who are randomized to ixekizumab 80 mg Q2W or ixekizumab 80 mg Q4W at Week 0 of the originating studies and consistently receive the same treatment regimen through Week 64 in RHBY. Patients who were randomized to placebo or adalimumab in any of the originating studies, patients who switched from IXEQ4W to open label to IXEQ2W during the originating study of RHBY, patients who were randomized to placebo during Period 2 of RHBY, and patients who were retreated during Period 2 of RHBY are not included in this population. Patients will be analyzed according to the ixekizumab regimen they were randomized to at Week 0 of the originating study.

**Ixekizumab Structure Population:** The analysis of 2-year radiographic progression in spine, measured by the change in mSASSS in patients with active rad-axSpA, will be conducted on Ixekizumab Structure Population, defined as all patients who i) are from either RHBV or RHBW study; and ii) have mSASSS data at both Week 0 in the originating study and Week 56 in RHBY.

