**Randomized Withdrawal (RW) Intent-to-Treat (ITT) Population:** Efficacy and health outcome analyses for Period 2 will be conducted on RW ITT Population, defined as all patients who achieved a state of sustained remission and were randomized to 40-week double-blind placebo-controlled RWR period (Group B), even if the patient does not receive the correct treatment or otherwise does not follow the protocol. Patients will be analyzed according to the treatment to which they are assigned.

**RW Safety Population:** Safety analyses will be conducted on the RW Safety Population, defined as all randomized patients in Group B who have received at least 1 dose of study

treatment after randomization in the specified period. Patients will be analyzed according to the treatment to which they are assigned.

**Flare Population:** Defined as all randomized patients in Group B who experience a flare after randomization at Week 24. Efficacy summaries will be conducted for Period 2 and Combined Periods 2 and 3 on the Flare Population who receive at least one injection of ixekizumab retreatment after flare in the Combined Periods 2 and 3. Patients will be analyzed according to the treatment to which they are assigned at randomization and the retreatment.

**Dose Escalation Population:** Exploratory efficacy summaries will be conducted for Period 3 on Dose Escalation Population, defined as all patients (from Group A and Group B) who have been treated ixekizumab 80 mg Q4W for at least 12 weeks, and had their dose escalated to ixekizumab 80 mg Q2W (determined by investigator).

**Follow-Up Period Population:** Safety analysis for Period 4 will be conducted on the Follow-Up Period Population, defined as all patients who have completed an originating study (RHBV, RHBW, or RHBX) through Week 52 and have entered the Post-Treatment Follow-Up Period (Period 4) in RHBY. Patients will be analyzed according to the treatment they are taking before entering Period 4.

[Table RHBY.6.1](#) displays analyses purpose and treatment groups for each analysis population and study period.

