**Table RHBY.6.1. Treatment Groups and Major Patient Populations for Analysis Periods for Study RHBY**

Population	Period	Analyses	Treatment Groups	Group Comparisons
Lead-In Period Safety Population	Combined Periods 1 & 2 Combined Periods 1, 2, & 3	Safety	IXE80Q2W IXE80Q4W Total IXE	Descriptive No inferential statistics
Long-Term Ixekizumab Treatment Efficacy Population	Combined Periods 1 & 2 Combined Periods 1, 2, & 3	Efficacy and health outcomes	IXE80Q2W a IXE80Q4W a Total IXE	Descriptive No inferential statistics
RW Safety Population	Period 2 Period 3	Safety	IXE80Q2W IXE80Q4W Total IXE Placebo	Total IXE vs. Placebo IXE80Q2W vs. Placebo IXE80Q4W vs. Placebo
RW ITT Population	Period 2 Combined Periods 2 & 3	Efficacy and health outcomes	IXE80Q2W IXE80Q4W Total IXE Placebo	Total IXE vs. Placebo IXE80Q2W vs. Placebo IXE80Q4W vs. Placebo
Ixekizumab Structure Population	At Week 56 for a 2-year assessment	Efficacy	IXE80Q2W IXE80Q4W Total IXE	Descriptive No inferential statistics
Flare Population with retreatment	Period 2, Combined Periods 2 and 3	Efficacy	PBO/IXE80Q2W PBO/IXE80Q4W PBO/IXE IXE80Q2W/IXE80Q2W IXE80Q4W/IXE80Q4W IXE/IXE	Descriptive No inferential statistics
Dose Escalation Population	Period 3	Efficacy	PBO/IXE80Q4W, IXE80Q4W/ IXE80Q4W Total	Descriptive No inferential statistics
Follow-Up Population	Period 4	Safety	IXE80Q2W IXE80Q4W Total IXE Placebo	Descriptive No inferential statistics

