### ***6.1.3. General Considerations for Analyses during the Extension Period Including the Double-Blind RW Period (Period 2)***

#### **6.1.3.1. RW ITT and RW Safety Populations**

For patients who are randomized in Period 2 (group B), comparisons between Combined Ixekizumab treatment group and placebo, as well as between each ixekizumab regimen (80 mg Q2W or 80 mg Q4W) and placebo, will be performed for all analyses at each scheduled visit in Period 2 including Visit 515 at Week 64.

Period 2 starts at the first injection of study treatment after randomization (at Week 24) and ends at the following study events:

- Prior to the first injection of study treatment at Week 64 (Visit 515) for not retreated patients who have completed visit at Week 64. If injection at Week 64 is missing, the next injection date after Week 64 is used;
- Prior to the first injection of retreatment for patients who have been retreated within Period 2;
- ETV prior to Week 64.

For patients who are in the RW ITT Population and have been retreated with the ixekizumab treatment regimen due to a flare or any other reasons, only data prior to the time of the retreatment will be included in the analysis for Period 2. Data after retreatment will be imputed using nonresponder imputation (NRI) method for categorical variables and mBOCF method for continuous variables.

The observed values after retreatment will be used for other specified analysis, for example, efficacy analysis for Flare Population with Retreatment.

For efficacy and health outcomes, baseline is defined as the last available value before the first dose of study treatment in Period 2 from the originating study and, in most cases, will be the value recorded at Week 0 from the originating study.

The primary analysis method for treatment comparisons of categorical binary efficacy and health outcome variables will be a logistic regression with treatment group, geographic region, and originating study as factors using PROC Logistic with Wald method. The odds ratio and 95% CIs will be reported; treatment difference and 95% CI will also be reported. In the case when logistic regression model does not produce statistical results due to sparse data, Fisher's exact test will be used. Same analysis will also be carried out at each of other scheduled visits in Period 2.

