### **6.1.3.2. Flare Population**

For patients who experienced a flare (Flare Population), a set of selected key efficacy outcomes at time of flare will be summarized.

For the Flare Population with Retreatment in Period 2, the period starts at the time of first injection of the retreatment of ixekizumab 80 mg Q2W or 80 mg Q4W following the flare and ends on the date of Period 2 defined in Section 6.1.3.1.

Summary statistics will be provided based on the Flare Population with Retreatment for a subset of efficacy outcomes: the proportion of patients who regain response in ASDAS <1.3, ASDAS <2.1, and who achieve/maintain an ASDAS<1.3, ASDAS<2.1, ASAS20, ASAS40, ASAS5/6, ASAS partial remission, ASDAS major improvement and clinically important improvement within 16 weeks after the ixekizumab retreatment for patients who have 16 weeks of retreatment. No inferential statistics will be provided. The Kaplan-Meier estimates of the proportion of patients who first regain response on the variables of interest will be carried out at each retreatment interval (4 weeks, 8 weeks, etc.) up to 40 weeks. If an ongoing patient has not regained response by 16 weeks or Week 64, the patient will be censored at 16 weeks and Week 64, respectively. For time to response through Week 64, if a patient discontinued the study prior to Week 64, the patient will be censored at the date of their last visit during Period 2.

For counting regaining a response, once a patient has a response, the status is cumulative and carried forward. This counting process starts at the first visit when the retreatment is initiated. For counting achieving/maintaining a response, the status may change with time and the status depends on the response at each visit and does not depend on the previous visit.

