## **6.11. Health Outcomes/Quality-of-Life Analyses**

The health outcomes and quality of life (QOL) measures are ASAS HI, SF-36, EQ-5D-5L, Fatigue NRS, JSEQ, WPAI-SpA, and Quick Inventory of Depressive Symptomatology—Self Report 16 items (QIDS-SR16).

The analyses of health outcomes and QOL measures will be carried out for the RW ITT Population during Period 2 and for the Long-Term Ixekizumab Treatment Population during the Combined Periods 1 and 2, and Combined Periods 1, 2, and 3. There will be no adjustment for multiple comparisons for RW ITT Population during Period 2.

[Table RHBY.6.6](#) includes the description and derivation of the health outcomes and QOL measures.

[Table RHBY.6.7](#) provides the detailed analyses including measurement, variables, analysis method and imputation method, population, treatment group comparisons, and time points for health outcomes and QOL analyses.

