#### **6.13.8.2.3. Analyses of Treatment-Emergent ADA on Specific Adverse Events**

The analyses of TE-ADA on specific adverse events will be conducted on all evaluable patients within the Lead-In Period Safety Population during Combined Periods 1 and 2, and Combined Periods 1, 2, and 3, and for RW Safety Population during Period 2. For Lead-In Period Safety Population during the combined periods, all data are included regardless of treatment changes.

Adverse events of special interest, allergic reaction/hypersensitivity (anaphylaxis and non-anaphylaxis) and of injection-site reactions, will be included in an assessment of AE to TE-ADA over time. Timing of an AE will be taken to be the reported AE start date.

For each TE-ADA status dichotomous variable (as defined in [Table RHBY.6.10](#)), patients will be categorized according to whether they were (i) always in lesser-TE-ADA status postbaseline or (ii) at least once in greater-TE-ADA status postbaseline. For each AESI, within the time-varying TE-ADA status groups, a summary will be provided of the number of patients who had no event, events only while in lesser-TE-ADA status for group (i), or – for group (ii) – at least 1 event while in greater-TE-ADA status.

Additionally, summaries will be provided of the total number of AESI events (with unique start dates) by time-varying TE-ADA status groups at the event date. The summaries will aggregate time respectively in greater-TE-ADA status and in lesser-TE-ADA status, along with the event rates (rates per 100 patient-years) relative to those aggregate times.

By-patient listings will be provided of patients with TE-ADA who experience a treatment-emergent allergic reaction/hypersensitivity reaction or an injection site reaction.

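### The protocol promises a descriptive safety and health-outcome summary for patients who flare in Period 2, but the visible SAP gives the retreated flare population outcome summaries for efficacy only.

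*SAP*

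**What the plan says.** Protocol 10.3.1.2.1, repeated in the synopsis, says that for randomized patients who flare in Period 2, "efficacy, health outcomes, and safety data collected between time of flare and the end of Period 2 will be summarized" for each ixekizumab regimen, without inferential statistics.

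The SAP's provisions for the same patients are these:

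- **Population (6.1.1):** "Efficacy summaries will be conducted for Period 2 and Combined Periods 2 and 3 on the Flare Population who receive at least one injection" of retreatment.
- **Table RHBY.6.1:** the row "Flare Population with retreatment" has Efficacy as its only analysis type.
- **6.1.3.2:** "Summary statistics will be provided based on the Flare Population with Retreatment for a subset of efficacy outcomes". The outcomes named there are ASDAS and ASAS responses, and Table RHBY.6.5 lists the same kind.
- **Period 2 safety window (6.1.3.1):** for retreated patients Period 2 ends "Prior to the first injection of retreatment for patients who have been retreated within Period 2".
- **Combined-period safety (6.1.1, Lead-In Period Safety Population):** "Patients will be analyzed according to the treatment they were receiving at the start of Period 1". The columns are Q2W, Q4W and Total IXE. For antibody status and specific adverse events, 6.13.8.2.3 adds: "For Lead-In Period Safety Population during the combined periods, all data are included regardless of treatment changes".
- **Health outcomes (6.11):** "The analyses of health outcomes and QOL measures will be carried out for the RW ITT Population during Period 2", and otherwise only for the Long-Term Ixekizumab Treatment Efficacy Population.

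**The concern.** Withdrawal to placebo followed by re-exposure is the feature of this study that can inform on restarting ixekizumab. Protocol 3.3 names serious hypersensitivity as an important potential risk, and Protocol 9.2.2 lists allergic reactions and injection-site reactions as events of special interest. Efficacy of retreatment is a stated secondary objective. If the report shows how often response is regained, but not what happened to safety and quality of life after the restart, that account is one-sided and a written protocol commitment is left unmet.

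**Working it through.** **1. Where post-retreatment data go in the visible SAP**

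| Data after first retreatment injection | Planned place | Retreated patients visible as a group? |
|---|---|---|
| ASDAS and ASAS responses | Flare Population with Retreatment (6.1.3.2, Table RHBY.6.5) | Yes |
| Completion and reasons for stopping treatment; Week 24 characteristics | 6.6, 6.7 | Yes, but neither is a safety or health-outcome summary |
| Adverse events, Period 2 randomized comparison | RW Safety Population; window closes before retreatment (6.1.3.1) | Not included |
| Adverse events, combined periods | Lead-In Period Safety Population by Period 1 regimen (6.1.1, 6.1.2.1) | No, pooled |
| Adverse events, Period 3 overview | RW Safety Population as assigned (6.1.1, 6.13.2) | No; a retreated placebo patient could count under Placebo |
| Adverse events, structure overview | Ixekizumab Structure Population (6.13.2) | No, pooled |
| Health outcomes, RW ITT | Values after retreatment replaced by carry-forward (6.1.3.1, 6.3.3) | Not used |
| Health outcomes, Long-Term population | Patients randomized to placebo or retreated in Period 2 are excluded (6.1.1) | Not included |

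The last two rows close both routes for health outcomes. The one partial exception is QIDS-SR16, whose worst score also enters the pooled safety tables (6.13.6).

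**2. How many patients**

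The plan gives no figure for the retreated group. Its power statement supplies the inputs: 200 randomized 2:1, flare rates of 10% on ixekizumab and 70% on placebo (Protocol 10.1), and about 750 entrants (Protocol 5.2). That statement reproduces: exact two-sided Fisher power for 133 versus 67 exceeds 0.9999, against a stated value of over 99%.

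- Placebo flarers: 0.70 × 67 = 46.9, about 47.
- Ixekizumab flarers: 0.10 × 133 = 13.3, about 13.
- Share of the pooled tables: 46.9 / 750 = 6.3%.
- With 150 randomized (Protocol 10.1, 20% qualifying): 0.70 × 50 = 35, or 4.7% of 750.
- With 225 randomized (30% of 750 taken literally): 0.70 × 75 = 52.5, or 7.0%.

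These counts assume that every flarer is retreated.

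**3. What pooling does (illustration; the event risks are assumed, not in the documents)**

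Take a 5% risk in the other 703 patients.

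- Risk of 15% after re-exposure: (703 × 0.05 + 47 × 0.15) / 750 = 42.2 / 750 = 5.6%.
- Risk of 10% after re-exposure: (703 × 0.05 + 47 × 0.10) / 750 = 39.85 / 750 = 5.3%.

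By person-time, assume no dropout, 64 weeks for the 683 patients not randomized to placebo, 24 weeks for the 67 placebo patients before withdrawal, and w weeks of retreatment for 47. The re-exposed share is 47w / (683 × 64 + 67 × 24 + 47w). With w = 8 this is 376 / 45,696 = 0.8%; with w = 36 it is 1,692 / 47,012 = 3.6%.

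**4. What a comparison with retreated ixekizumab-arm flarers could show**

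With 47 versus 13 patients and assumed risks of 15% and 5%, two-sided Fisher power is 0.4%. The chance of no event among the 13 at a 5% risk is 0.95^13 = 51%.

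**The case against.** The case for leaving the SAP alone has several parts.

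- **Events are not lost.** All adverse events are listed by patient. Hypersensitivity and injection-site reactions have their own listings, and SAP 6.13.8.2.3 gives rates for them by time-varying antibody status. With about 47 patients, case-level review is feasible. This stands, so a reader who infers that re-exposure events go unrecorded is mistaken. A listing or a pooled rate is still not the promised summary.
- **The promise is narrow.** It runs from flare to the end of Period 2, by regimen. It does not mention separate columns by randomized arm, antibody results or Period 3. This also stands. A table by regimen alone would mix re-exposed placebo patients with ixekizumab-arm flarers, so separate columns are a recommendation beyond the commitment.
- **Other protocol text fits the SAP.** Protocol 10.3.4 does not name the flare population, the retreatment objective concerns efficacy only, and 10.3.1 lets non-principal analysis changes be justified in the study report. The visible SAP records no such justification.
- **SAP 6.1.3.1 is open-ended.** It reserves observed values after retreatment for other specified analyses and gives flare-population efficacy as an example. No safety or health-outcome analysis of that kind is specified in the visible text.
- **Redaction.** Parts of the SAP, including the exploratory section, are blacked out and could hold such a table. The finding can cover only what is visible.

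A reader might also infer that retreated ixekizumab-arm flarers are a ready control, so that the trial could show whether restarting is as safe as staying on. The documents do not support this. That group is about 13 patients selected by flaring on drug, retreatment is in general open-label, and the contrast is between groups formed after randomization.

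**Conclusion.** The mismatch is real but limited. The protocol commits to a descriptive safety and health-outcome summary after flare, and the visible SAP provides neither. The health-outcome gap is the clearest: apart from the pooled QIDS-SR16 safety tables, post-retreatment values are summarized nowhere visible. For safety, the events are planned to be reported, but pooled or under the assigned arm; the possible Placebo attribution in Period 3 is a second problem beside dilution.

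About 47 re-exposed placebo patients (35 to 53 across the plan's sample sizes) is an upper figure for the promised window. Protocol 7.4 starts Period 2 retreatment at the next scheduled visit, so some late flarers restart only in Period 3. The dilution figures show only how little a pooled rate would move under assumed risks; they are not evidence of a re-exposure risk. The primary and major secondary analyses are unaffected. The SAP should be amended, or the omission stated and justified.

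**What to change.** 1. In SAP Table RHBY.6.1, change the analysis entry for the Flare Population with retreatment to efficacy, health outcomes and safety.
2. In SAP 6.11 and 6.13, add descriptive summaries by regimen from first retreatment injection to the end of Period 2: health outcomes, TEAEs, SAEs, allergic reactions/hypersensitivity and injection-site reactions. Show the PBO/IXE columns already defined in Table RHBY.6.1 separately, with patient-years.
3. State in SAP 6.1.5.2 that Period 3 events in retreated placebo patients will not be shown under Placebo alone.
4. Optionally, extend the summaries to Combined Periods 2 and 3 and add TE-ADA.

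The cost is a few tables from data already collected. For placebo-arm patients the TEAE baseline at retreatment (6.1.2.1) and the retreatment exposure, duration 2 (6.13.1), are already derived; the same two derivations would have to be added for retreated ixekizumab-arm patients. The downside is small, non-randomized groups (about 47 and 13), so the tables should carry a note that they are descriptive and do not support a conclusion about restarting versus continuing.

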**Table RHBY.6.1. Treatment Groups and Major Patient Populations for Analysis Periods for Study RHBY**

Population	Period	Analyses	Treatment Groups	Group Comparisons
Lead-In Period Safety Population	Combined Periods 1 & 2 Combined Periods 1, 2, & 3	Safety	IXE80Q2W IXE80Q4W Total IXE	Descriptive No inferential statistics
Long-Term Ixekizumab Treatment Efficacy Population	Combined Periods 1 & 2 Combined Periods 1, 2, & 3	Efficacy and health outcomes	IXE80Q2W a IXE80Q4W a Total IXE	Descriptive No inferential statistics
RW Safety Population	Period 2 Period 3	Safety	IXE80Q2W IXE80Q4W Total IXE Placebo	Total IXE vs. Placebo IXE80Q2W vs. Placebo IXE80Q4W vs. Placebo
RW ITT Population	Period 2 Combined Periods 2 & 3	Efficacy and health outcomes	IXE80Q2W IXE80Q4W Total IXE Placebo	Total IXE vs. Placebo IXE80Q2W vs. Placebo IXE80Q4W vs. Placebo
Ixekizumab Structure Population	At Week 56 for a 2-year assessment	Efficacy	IXE80Q2W IXE80Q4W Total IXE	Descriptive No inferential statistics
Flare Population with retreatment	Period 2, Combined Periods 2 and 3	Efficacy	PBO/IXE80Q2W PBO/IXE80Q4W PBO/IXE IXE80Q2W/IXE80Q2W IXE80Q4W/IXE80Q4W IXE/IXE	Descriptive No inferential statistics
Dose Escalation Population	Period 3	Efficacy	PBO/IXE80Q4W, IXE80Q4W/ IXE80Q4W Total	Descriptive No inferential statistics
Follow-Up Population	Period 4	Safety	IXE80Q2W IXE80Q4W Total IXE Placebo	Descriptive No inferential statistics

